Study Protocol

Otological Safety Profile of 100% Manuka Honey Application in Tympanoplasty: A Double-blinded Randomized Controlled Trial

Formulated on 5th May 2021

Revised on 20th November 2022

Background

Chronic suppurative otitis media (CSOM) is the chronic inflammation of the middle ear mucosa characterized by intermittent or continuous ototorhea from the ear canal that can be mucopurulent or serous in nature, through a perforation of the tympanic membrane that has occurred for two months or more. Two types of CSOM are recognized, a mucosal disease (safe type) and an epithelial disease (unsafe type).^{1,2}

CSOM is included in the ten most commonly found diseases in the field of Ear Nose Throat Head and Neck Surgery (ENT-HNS) in Indonesia, and ranks first in its prevalence. The prevalence of CSOM in Indonesia based on a survey by the Ministry of Health of the Republic of Indonesia in 1993-1996 was 3.1%,³ and according to the criteria of the World Health Organization (WHO) Indonesia was considered to have a high prevalence rate. When calculated based on the total population of Indonesia, which is currently 250 million, it is estimated that Indonesia has 7.8 million people who suffer from CSOM. Patient data from the Otology Division of the ENT-KL National Hospital [name] (RSCM) for the 2010-2020 period also showed a similar value, where CSOM was the number one cause of patient visits to the outpatient clinic and the most surgeries carried out each year.⁴ The impact caused by CSOM is very large, namely hearing loss, restrictions on activities related to water, as well as the risk of fatal complications.¹

Developments in the field of ENT-KL, especially otology, have made this disease treatable with a high success rate. One of the therapeutic options for CSOM is middle ear surgery. The aim of this surgery the prevention of reinfection through closure of the TM. However, graft failures can still occur. This failure can be caused by poor vascularization around the edge of the perforation due to chronic infection that results in low secretion of growth factors needed for the wound healing.

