
Research Objectives

- To test the otological safety of 100% medical grade manuka honey given at the time of tympanoplasty.

Research Design

This study uses a comparative, randomized and prospective clinical trial design to determine the effect of honey in increasing tympanic membrane re-epithelialization post tympanoplasty. The clinical study uses 100% medical grade manuka honey to determine the safety of its use in the healing process of tympanic membrane perforation after tympanoplasty. The subjects of the clinical study are CSOM patients of the mucosal type who underwent tympanoplasty at the Cipto Mangunkusumo hospital. During this research procedure, evaluation of the effect of ototoxicity will be carried out on all patients with the click stimulated ABR starting from the first subject. If an ototoxicity effect is indeed found, it will immediately be reported to an independent team outside the research team for an interim analysis to see the causal relationship with the treatment. Other side effects of administering manuka honey during and after the study reported by patients were immediately noted and evaluated.

Methods

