The in vivo study was a randomized, controlled, double-blind clinical trial on adult patients (18 - <46 years old) diagnosed with tubotympanic chronic suppurative otitis media (CSOM) undergoing tympanoplasty at Cipto Mangunkusumo General Hospital (CMGH) from June 2021 – August 2022. Patients who had previously received surgical treatment for CSOM in the same ear or had recurrent or residual disease and those whose pathology showed suspicion of tumors were excluded from the study. Patients were randomly divided into intervention and control groups using the Robust Randomization App (RRApp)¹²² with a simple random sampling method and a ratio of 1: 1. Patients were blinded to the group assignments. During tympanoplasty, after filling the middle ear with gel foam and placing the graft, gel foam soaked in MH (MANUKApli topical gel, ManukaMed®) was placed in the external ear canal in the intervention group, while the control group only received a gel foam packing. The outer third of the ear canal was filled with an antibiotic tampon. The ear tampon is removed two weeks after the procedure and all patients applied six drops of 0.3% of ofloxacin twice daily for five days. Patient's symptoms were followed up at a weekly basis for the duration of six weeks. The BERA test was done at week 5. An audiometry test was done at week 6 to evaluate possible hearing loss. At 3 to 6 weeks post-tympanoplasty, patients were not given any ear drops.

For the in vivo study, the Mann-Whitney U test was used for unnormalized distributed continuous data. Categorical data were analyzed by using the Chi-square test with an alternative Fisher's exact test. The correlation of two numerical variables was analyzed by the Pearson correlation test for normally distributed data and Spearman correlation for data with non-normal distribution. The normality test was the coefficient of variation (COV) and the Shapiro-Wilk test. All tests were carried out in two-tailed with a significance level of 0.05. All data were processed and analyzed using Microsoft Excel 2021 and the Statistical Package for The Social Sciences (SPSS) version 26. All graphs were created using GraphPad Prism 9.1.0. This study was approved by the ethical committee of the Faculty of Medicine, Universitas Indonesia (no. KET 469/UN2.F1/ETIK/PPM.00.02/2021).

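### Otological safety is the only listed objective, but the plan has only difference tests: no effect estimate, confidence interval, acceptable-loss limit or sample size, so a non-significant result cannot support safety

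*Combined protocol and SAP*

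**What the plan says.** Research Objectives in the combined protocol and SAP contains a single item: "To test the otological safety of 100% medical grade manuka honey given at the time of tympanoplasty". The Research Design text adds an efficacy aim, "to determine the effect of honey in increasing tympanic membrane re-epithelialization post tympanoplasty", but does not list it as an objective.

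The safety data described in Methods are a BERA test at week 5, weekly symptom follow-up for six weeks, and audiometry: "An audiometry test was done at week 6 to evaluate possible hearing loss". Research Design adds that side effects reported by patients are noted and evaluated.

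The analysis of these data is one paragraph at the end of Methods. For continuous outcomes: "For the in vivo study, the Mann-Whitney U test was used for unnormalized distributed continuous data". For categorical outcomes: "Categorical data were analyzed by using the Chi-square test with an alternative Fisher's exact test". Pearson or Spearman correlation and normality checks complete the list. "All tests were carried out in two-tailed with a significance level of 0.05".

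Research Design has one further safety provision. Click ABR is done in all patients from the first subject, and "If an ototoxicity effect is indeed found, it will immediately be reported to an independent team outside the research team", which then makes an interim analysis of causality.

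**The concern.** To conclude that a treatment is safe, harm of some stated size has to be excluded. A test of no difference does not do this. A significant result points to a difference. A non-significant one is equally compatible with no harm and with harm that the trial was too small or too variable to see. A confidence interval would separate these cases, but none is planned. A sample size justified against a stated loss would at least show what the trial could see, and that is missing too.

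If the safety tests are non-significant, the plan therefore gives no basis for answering its only listed objective. A reader could not tell a trial that ruled out a material hearing loss from one that could not have found it. The significance level and the two-sided testing are not at fault, and difference tests are suitable for the re-epithelialization aim.

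**Working it through.** **Inputs from the documents.** Allocation 1:1; two-sided 0.05; Mann-Whitney, Chi-square or Fisher. No sample size, power, SD, event rate, margin or definition of ototoxicity is stated, so there is no planned figure to reproduce. Every n, SD and effect below is an assumption used to show a range, not a proposal.

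**1. How much observed harm stays non-significant.** With x of n honey patients affected and 0 of n controls, the two-sided Fisher p-value is 2·C(n,x)/C(2n,x). For 4/20 against 0/20 this is 2 × 4845/91390 = 0.106.

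| n per arm | Largest non-significant count | p | Smallest significant count |
|---|---|---|---|
| 10 | 4 | 0.087 | 5 |
| 20 | 4 | 0.106 | 5 |
| 30 | 5 | 0.052 | 6 |
| 50 | 5 | 0.056 | 6 |

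The Newcombe 95% interval for 4/20 against 0/20 runs from -0.1% to 41.6%. The p-value shows none of this.

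**2. How often true harm is missed, binary outcome.** With no events in controls, the miss rate is P(X ≤ c), where X is binomial(n, true risk) and c is the largest non-significant count above.

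| True risk, honey vs control | n=10 | n=20 | n=30 | n=50 |
|---|---|---|---|---|
| 20% vs 0% | 96.7% | 63.0% | 42.8% | 4.8% |
| 10% vs 0% | 99.8% | 95.7% | 92.7% | 61.6% |

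The pattern does not depend on an event-free control arm. For 15% against 5%, exact Fisher power is 7%, 9%, 24% and 59% at n = 20, 30, 50 and 100 per arm, so this harm is missed 93%, 91%, 76% and 41% of the time.

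**3. How often true harm is missed, continuous outcome.** Mann-Whitney, true shift of 10 dB, normal data, 10,000 simulated trials per cell.

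| SD | n=10 | n=20 | n=30 | n=50 |
|---|---|---|---|---|
| 10 dB | 48% | 15% | 4% | <1% |
| 15 dB | 74% | 50% | 31% | 10% |
| 20 dB | 84% | 68% | 55% | 32% |

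**4. What an interval would add.** With n = 20 per arm and SD 15 dB, the simulated mean half-width of the 95% Hodges-Lehmann interval is about 10 dB. The normal approximation gives a similar value: 1.96 × 15 × √(2/20) = 9.3 dB. An observed difference of exactly 0 dB would then still not exclude a loss of about 10 dB. With n = 50 and SD 10 dB the half-width falls to about 4 dB.

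**5. No events at all.** The one-sided 95% upper limit for 0/n is 1 − 0.05^(1/n): 25.9%, 13.9%, 9.5% and 5.8% for n = 10, 20, 30 and 50. This bounds the risk in the honey arm alone; it is not a comparison with control.

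**The case against.** The strongest reply is that the plan never says p > 0.05 will be read as safe. Testing safety could mean looking for harm, and difference tests do that. This is fair as far as it goes, but under that reading the plan still has no criterion by which safety could be concluded.

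Second, the safeguard in Research Design is real: ABR in every patient, with review outside the research team. It reduces the risk to individual patients. It does not fill the gap, because it starts only once an ototoxicity effect has been found, that term is undefined, and the review concerns the cause of cases already seen. It supplies no group-level rule.

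Third, the text may be an extract of a longer work: reference numbers jump from 19 to 122, and Methods is written in the past tense. A sample size calculation may exist elsewhere, and a paragraph naming tests does not prohibit reporting intervals. That cannot be ruled out. However, the statistical paragraph reads without a break and refers to no other document.

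Fourth, the size of the problem is wholly assumed and ranges from trivial to severe. That stands, and the figures above are illustration only.

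Finally, Methods names no between-arm test for normally distributed continuous data, so an interval tied to Mann-Whitney might seem to leave a hole. It need not, because a Hodges-Lehmann interval does not require non-normal data.

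**Conclusion.** The concern holds. The only listed objective has no decision rule, and the analyses named for it cannot turn a null result into evidence of safety. This follows from the text alone and needs no assumed figure.

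How much it matters in practice depends on the number of patients and the variability, neither of which the documents give. For a small or variable trial the gap is large: with 20 per arm, a 20% against 0% risk is missed 63% of the time, and a 10 dB shift at SD 15 about half the time. For a larger, less variable trial it can be small: with 50 per arm the same risk difference is missed 5% of the time, and a 10 dB shift at SD 10 less than 1%. The gap must be closed before any safety conclusion is drawn.

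**What to change.** Keep the tests, but for week-5 BERA, week-6 audiometry and adverse events make the honey-minus-control difference with a 95% confidence interval the main result:

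- Continuous measures: a Hodges-Lehmann estimate and interval, whether or not the data pass the normality check.
- Binary outcomes: the risk difference with an exact or score interval.
- Baseline hearing: adjust for it only if a baseline test exists; the documents state none.

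Do not conclude safety from p > 0.05. Claim it only if the interval excludes a largest acceptable loss that the investigators fixed before unblinding. Recruitment ended in August 2022 and the title block reads "Revised on 20th November 2022", so this may no longer be possible. If no limit was fixed, or the data are already unblinded, set none afterwards. State instead that no difference was detected and that losses up to the interval's limit, in dB or percentage points, are not excluded.

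Report the independent team's case reviews separately, with the definition of ototoxicity that was used.

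The cost is a few sentences of analysis text and interval estimates from data already collected, with no new patients or visits. A sample size rationale cannot be supplied afterwards, but the interval's width will show what the achieved sample could exclude. The drawback for the sponsor is that the safety statement may be weaker than a bare p-value would suggest.
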